Deterministic tractography of diffusion data will be conducted with DSI Studio (<http://dsi-studio.labsolver.org/>). The generalized q-sampling algorithm will be used for fiber reconstruction. This algorithm permits estimation of multiple fibers per voxel improving reconstruction accuracy in areas rich in crossing fibers [82]. Fiber streamlines will be estimated from "seed" ROIs and then filtered to exclude streamlines passing through, but not ending in, target ROIs. If the seed is in striatum, targets will be located in VMPFC/orbitofrontal cortex, or vice versa. To test the hypothesis that white matter pathways connecting VMPFC-to-striatum are compromised in Veterans with STBs, individual-level track statistics (anisotropy, density) will be entered into MATLAB ANCOVA models.

Differences in fMRI activation during decision-making between Veterans with/out STBs.

These analyses test the hypothesis that neural signals in the striatal-to-VMPFC circuit related to rewards and decision-making are attenuated in Veterans with STBs. Preprocessed fMRI data from the reward expectancy task will be used for these analyses. Whole-brain first-level fixed-effect GLMs will be constructed for each subject with SPM12. A parametric regressor will be used to model univariate fMRI activation related to reward expectancy.

Parametric values are set to +0.5 for probable wins, -0.375 for probable losses, +0.125 for ambiguous cues, and zero for the neutral cues (see D5.5.2) [83]. Separate regressors for positive (better than expected) and negative (worse than expected) prediction errors will also be constructed. GLMs will be created by convolving the canonical hemodynamic response function with regressors of interest and nuisance regressors (motion parameters and derivatives, mean signal in cerebrospinal fluid). Subjects will be treated as random effects in second-level univariate fMRI models. To evaluate whether reward-related signals are blunted in Veteran with STBs, the averaged blood oxygen level-dependent (BOLD) signal for our conditions of interest will be extracted from VMPFC and striatal ROIs and contrasted between groups. Whole-brain statistical maps for reward expectancy and prediction errors will also be contrasted between Veterans with STBs and controls.

Statistically significant clusters from this univariate whole-brain analysis may be used as ROIs in functional connectivity models below.

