Differences in functional connectivity between Veterans with STBs and controls.

These analyses test the hypothesis that the VMPFC-to-striatal decision-making circuit is less functionally cohesive in Veterans with STBs. Functional connectivity analyses of both task (reward expectancy) and resting-state will be conducted using the CONN Toolbox.⁵⁰

Unsmoothed residual BOLD time courses will be extracted from each subjects' preprocessed data and then cross-correlated. The resulting correlations will be converted to z-scores via Fisher's R-to-Z transformation in order to improve conformation to the assumptions of the GLMs used for seed-based hypothesis testing. Z-scores will be entered into GLMs comparing VMPFC-to-striatal connectivity between groups. For task-based functional connectivity, a weighted GLM approach will be used to compare connectivity during the expected reward and prediction error task conditions of between Veterans with and without STBs. Additional analyses using ROIs functionally-defined in the univariate analysis described above as seeds may also be run.

Design Considerations & Alternative Outcomes: This hypothesis testing sequence focuses on the VMPFC-to-striatum decision-making circuit. However, effects may be mediated by regions outside this *a priori* network e.g. in the amygdala-to-VMPFC circuit implicated in bipolar disorder with suicidality [85]. The role of this circuit could be explored should we fail to reject the null hypothesis. Alternatively, a data-driven method such as multi-voxel pattern analysis could be used to functionally identify neural circuits differing between Veterans with and without STBs.

E3.2 Evaluate whether correlates of decision-making and cognitive control indicate risk severity.

Hypotheses: Decision-making will be less risky and/or impulsive in higher- vs. lower- risk Veterans with STBs. Structural and functional integrity of cognitive control regions will be superior in higher-risk Veterans with STBs.

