E3.4.5 Functional connectivity preprocessing. The following additional subject-level steps carried out with CONN reduce the impact of motion-related artifacts and non-neuronal signal on functional connectivity estimates [100-102]. The anatomical CompCor (aCompCor) routine (implemented in CONN) is an effective method for removing motion-related artefact that does not involve global signal regression [103], a practice that complicates interpretation of correlations [104,105]. Five principal components are extracted from the averaged fMRI signal in each aCompCor compartment (white matter, CSF). Principle components are regressed from subject-level data, along with regressors for linear trend, six estimated motion parameters and their 1st derivatives, and flagged high-motion or high global signal variance time points to limit potential sources of spurious variance. Residuals will be band-pass filtered (high-pass = 0.008, low-pass = 0.15) after confound regression [106].

E3.4.6 Diffusion MRI preprocessing: Preprocessing steps include: eddy-current compensation, head motion estimation and correction, and intra-subject registration. Diffusion preprocessing will be carried out using either FSL or FreeSurfer.

F. PRIVACY, CONFIDENTIALITY, & INFORMATION SECURITY

F1. Privacy interests and confidentiality

Minimizing risk of loss of Protected Health Information (PHI) is a priority of the proposed study. In accordance with VA guidelines and laws of the State of Rhode Island and Providence Plantations, confidentiality of the participants and their information will be upheld as outlined in this document. In agreement with the Department of Veterans Affairs Record Control Schedule 10-1, records will be maintained as outlined in this document. All documentation and data obtained over the course of this study will be stored as outlined in this document.

To protect participants' confidentiality, study participants will be assigned a numerical code that contains no personal identifiers or PHI. Participants will be listed only by this unique participant identification code on data files and data capture forms to maintain their anonymity. Codes will be sequential in numbering, e.g. 7001, 7002, 7003 etc. Identification codes will be applied to all cognitive testing, assessments, health service utilization, and MRI data collected over the course of the study.

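### Reward-task connectivity: the listed confound regression leaves the task-evoked response in the data, so a group difference in activation can appear as a difference in VMPFC-striatal connectivity

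*Combined protocol and SAP*

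**What the plan says.** The connectivity part of E3.1 puts two kinds of data through one pipeline: "Functional connectivity analyses of both task (reward expectancy) and resting-state will be conducted using the CONN Toolbox". The input to the correlations is described once for both: "Unsmoothed residual BOLD time courses will be extracted from each subjects' preprocessed data and then cross-correlated". For the task runs it adds that "a weighted GLM approach will be used to compare connectivity during the expected reward and prediction error task conditions" between Veterans with and without STBs.

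E3.4.5 defines the residuals. After the aCompCor components are extracted, "Principle components are regressed from subject-level data, along with regressors for linear trend, six estimated motion parameters and their 1st derivatives". The only other item removed is the set of volumes marked as artefact because of head movement or unstable global signal. A filter follows: "Residuals will be band-pass filtered (high-pass = 0.008, low-pass = 0.15) after confound regression". The list ends there.

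Task regressors appear only in the activation part of E3.1, for example: "A parametric regressor will be used to model univariate fMRI activation related to reward expectancy". Under E3.4.4 the univariate analyses run on data smoothed at 4 mm, whereas the connectivity data are unsmoothed. The connectivity residuals are therefore not described as residuals from the activation model.

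E3.1 makes two predictions about the same circuit. One is that "neural signals in the striatal-to-VMPFC circuit related to rewards and decision-making are attenuated in Veterans with STBs". The other is that VMPFC and striatum are less tightly connected in that group.

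**The concern.** The E3.4.5 list suits resting-state data. In the reward task, two regions that both respond to the same cue or feedback rise and fall together because they share a stimulus, whether or not they are coupled. If that shared response is not removed, it adds to the correlation in proportion to its size. A group with a weaker response then gets a different connectivity score with no difference in coupling.

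Here the plan expects exactly such an activation difference, in the same group and circuit. A task-connectivity finding could therefore be activation measured a second time but reported as a separate circuit finding.

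**Working it through.** **Inputs from the plan**
- Task: two runs of 48 trials (D4.3.4e); 480 s and 480 volumes per run (Table 4), although the task description gives 7 minutes.
- Filter: 0.008 to 0.15, taken as Hz (E3.4.5).
- Groups: up to 60 controls and up to 30 + 30 Veterans with STBs (participant groups under E3.1).
- Test: two-tailed 0.05, Bonferroni-corrected for the number of ROI comparisons (E3.1, MRI analyses).

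**The plan's own figure.** The only power statement for these contrasts is 85% for effect size 0.4, N = 72, three groups and two covariates. With noncentrality 0.4² × 72 = 11.52 on 2 and 67 degrees of freedom, power is 85.3%, so it reproduces. The point below does not depend on it.

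**Step 1: does the filter remove the evoked response?** The trial rate is 48/480 = 0.100 Hz, or 48/420 = 0.114 Hz with 7-minute runs. Both lie inside the pass band. In simulation about 94% of evoked variance survived the filter.

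**Step 2: effect on the correlation.** Let each region carry background signal with SD 1 and true correlation r, plus a shared evoked response with SD a. Before filtering:
- same sign: correlation = (r + a²)/(1 + a²)
- opposite sign: correlation = (r − a²)/(1 + a²)

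With r = 0.3 in both groups (assumed):

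| Control a | Sign | Controls | 30% weaker | 50% weaker |
|---|---|---|---|---|
| 0.3 | same | 0.39/1.09 = 0.358 | 0.3441/1.0441 = 0.330 | 0.3225/1.0225 = 0.315 |
| 0.5 | same | 0.55/1.25 = 0.440 | 0.4225/1.1225 = 0.376 | 0.3625/1.0625 = 0.341 |
| 0.5 | opposite | 0.05/1.25 = 0.040 | – | 0.2375/1.0625 = 0.224 |

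True coupling is the same in every cell.

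**Step 3: false rejection.** Simulations used two 480-volume runs, the 0.008–0.15 Hz filter, identical true coupling, 60 versus 60, two-sided 0.05 and no Bonferroni. Evoked ratios, coupling and activation deficits are assumptions.

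*Simulation A* (coupling 0.2; correlation weighted to win cues):

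| Evoked ratio | 30% weaker | 50% weaker |
|---|---|---|
| 0.3 | 24% | 48% |
| 0.5 | 50% | 91% |

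*Simulation B* (coupling about 0.3, between-person SD 0.2 on Fisher z, linear trend plus 22 nuisance regressors). Ranges cover whole-run, cue-weighted and prediction-error-weighted estimates:

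| Evoked ratio | 25% weaker | 50% weaker |
|---|---|---|
| 0.2 | 10–12% | 21–26% |
| 0.3 | 27–32% | 63–73% |
| 0.5 | 78–82% | about 100% |

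A further run at ratios 0.3–0.5 and 30–50% weaker activation gave about 17% to 100%. Equal activation gave about 5% in A and B. Condition weighting did not remove the bias.

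**Step 4: direction.** With opposite signs (ratio 0.5, 50% weaker), simulation B gave r = −0.09 in controls and 0.17 in the STB group, so the bias reverses.

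**Step 5: planned correction and smaller groups.** Rejection of 24% and 50% at 60 versus 60 corresponds to d = 0.23 and 0.36. The numbers of comparisons below are assumed.

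| Setting | d = 0.23 | d = 0.36 |
|---|---|---|
| 60 v 60, 3 comparisons | 13% | 33% |
| 60 v 60, 6 comparisons | 8% | 25% |
| 48 v 24, 3 comparisons | 7% | 16% |

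In the run that gave 17% to 100%, testing at 0.05/6 gave 5% to 98%.

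**Step 6: after removing task regressors.** Rejection fell to 5.2–5.7% (A) and 4–5% (B). That is the best case, because in B the regressors removed match the simulated response. When response delay varied between runs (SD 1 s, assumed), canonical regressors left 16% (ratio 0.3) and 77% (ratio 0.5) at 50% weaker activation. Another run left up to about 21%.

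**The case against.** The strongest reply is that this is an omission. E3.4.5 is about motion and non-neuronal signal and does not claim to be the whole task-connectivity model. The software list in F6.3 says that CONN handles task designs, so condition effects might be removed in a step that is not written down. A reader might infer that the evoked response will certainly remain in the data. The documents do not support that. They do itemise every other regressor, however, and the general description of CONN does not say that condition effects are removed. An analyst who follows the text gets the confounded contrast.

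A reader might also infer that any activation deficit must lower connectivity. That fails when the regions respond with opposite signs. If only one region is 30% weaker (ratio 0.3), simulated rejection is about 8–9%.

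The percentages are illustrations, not estimates for this trial. They use the maximum group sizes and no Bonferroni correction, and they vary with the assumed spread of coupling. In one run at ratio 0.3 and 50% weaker activation, adding between-person SD 0.2 on z cut rejection from 80% to 31%.

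Finally, the STB-versus-control contrast is listed as exploratory in A5, and E3.1 also tests the circuit at rest and by tractography. It would be wrong to conclude that the whole circuit hypothesis lacks independent evidence. All of these limits stand. None removes the mechanism for the task contrast.

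**Conclusion.** The point holds for reward-task connectivity only. Under the written confound list, a group difference in activation can register as a group difference in VMPFC-striatal connectivity with identical coupling. Connectivity is lower in Veterans with STBs if both regions respond with the same sign, and the reverse if the signs are opposite.

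The stated range of roughly 17% to near 100% false rejection rests on assumed evoked ratios of 0.3–0.5, activation 30–50% weaker, same-sign responses in both regions, 60 per group and no multiplicity correction. Bonferroni correction or smaller groups lower the rejection rate but leave the bias in the estimate. As the plan stands, a task-connectivity difference could not be told apart from an activation difference.

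**What to change.** In E3.4.5, for reward-task runs only, state that HRF-convolved task regressors are included in the confound regression before condition-weighted connectivity is computed. They should cover:
- the expectancy and positive and negative prediction-error regressors already specified for the activation model in E3.1;
- the remaining trial phases described in D4.3.4e (guess, cue, number, feedback), which still have to be built;
- preferably temporal derivatives or a flexible response basis, to limit the bias left by variable response timing.

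Report task connectivity alongside ROI activation, so that readers can see whether the two move together. Leave the resting-state list unchanged. If an unlisted step already removes condition effects, say so and specify it.

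The cost is a short addition to the text, minor analysis work and a small loss of residual degrees of freedom out of 480 volumes per run. No new data are needed.
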